#### **8.3.4. Reactogenicity Electronic Diary (Reactogenicity Subset Participants Only)**

Participants in the reactogenicity subset will be required to complete a reactogenicity e-diary through an application installed on a provisioned device or on the participant's own personal device. These participants will be asked to monitor and record local reactions, systemic

events, and use of antipyretic medication for 7 days, where Day 1 is the day of study intervention administration.

The reactogenicity e-diary allows recording of these assessments only within a fixed time window, thus providing the accurate representation of the participant's experience at that time. Data on local reactions and systemic events reported in the reactogenicity e-diary will be transferred electronically to a third-party vendor, where they will be available for review by investigators and the Pfizer clinicians at all times via an internet-based portal.

At intervals agreed to by the vendor and Pfizer, these data will be transferred electronically into Pfizer's database for analysis and reporting. These data do not need to be reported by the investigator in the CRF.

Investigators (or a designee) will be required to review the reactogenicity e-diary data online at frequent intervals as part of the ongoing safety review.

The investigator or designee must obtain stop dates from the participant for any ongoing local reactions, systemic events, or use of antipyretic medication on the last day that the reactogenicity e-diary was completed. The stop dates should be documented in the source documents and the information entered in the CRF.

All other participants will not complete a reactogenicity e-diary but will have their local reactions and systemic events detected and reported as AEs in accordance with [Section 8.4.2](#).

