#### **8.3.4.2. Local Reactions**

During the reactogenicity e-diary reporting period, participants will be asked to assess redness, swelling, and pain at the injection site and to record the symptoms in the reactogenicity e-diary. If a local reaction persists beyond the end of the reactogenicity e-diary period following vaccination, the participant will be requested to report that information and the corresponding resolution date. The investigator will enter this resolution date in the CRF.

Participants will be provided with a measuring device. Redness and swelling will be measured and recorded in **CCI** and then categorized during analysis as absent, mild, moderate, or severe based on the grading scale in [Table 2](#).

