#### **8.10.4. Visit 3 – 4-Week Follow-Up Visit (After Vaccination) – 28 to 35 Days After Visit 1**

Visit 3 may be completed as a home health visit (see [Section 8.1.2](#)).

- Record AEs as described in [Section 8.4](#).
- Record nonstudy vaccinations as described in [Section 6.9](#).
- Record prohibited medication use as described in [Section 6.9.1](#).
- If applicable, discuss contraceptive use as described in [Section 4.2.2](#).
- For participants in the immunogenicity subset, collect a blood sample of approximately 15 mL for immunogenicity testing. Alternatively, if the participant has consented to do so, collect a blood sample of approximately 50 mL, rather than 15 mL, for immunogenicity assessment/assay development.
  - If the participant has consented to do so, collect a blood sample (50 mL) for [CCI](#) [REDACTED]
- For participants in the reactogenicity subset, review the participant's reactogenicity e-diary data. Collect stop dates of any reactogenicity e-diary events ongoing on the last day that the reactogenicity e-diary was completed and record stop dates in the CRF if required.
- Ask the participant to contact the site staff or investigator if a medically attended event (eg, doctor's visit, emergency room visit) or hospitalization occurs.
- Ask the participant to contact the site staff or investigator (this could be via the ILI e-diary) immediately if he or she experiences any ILI symptoms as detailed in [Section 8.10.6](#).
- Record any AEs that occur within the 48 hours after the blood draw as described in [Section 8.4](#).
- Schedule an appointment for the participant to return for the next study visit.
- Complete the source documents.
- The investigator or an authorized designee completes the CRFs.

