For each local reaction reported for each vaccination, the maximum severity grade will be derived for the e-diary collection period (Day 1 through Day 7, where Day 1 is the day of each vaccination) as follows:

maximum severity grade = highest grade (maximum severity) within 7 days after vaccination (Day 1 through Day 7) among severity grades where the answers are neither "no" nor missing for at least 1 day during the interval from Day 1 through Day 7.

Duration of Each Local Reaction (First to Last Day Reported)

For participants experiencing any local reactions (or those with a derived reaction as described in [Table 4](#)), the maximum duration (resolution date of reaction - start date of reaction + 1) will be derived for each study vaccination.

Resolution of the reaction is the last day on which the reaction is recorded in the e-diary or AE CRF, or if it is unresolved during the participant e-diary recording period, the date the reaction ends (end date collected on the CRF) or AE stop date, whichever is longer, unless chronicity is established. If there is no known end date, the duration will be considered unknown and set to “missing.” Participants with no reported reactions have no duration.

Onset Day of Each Local Reaction

The onset day of each local reaction will be derived. Onset day is defined as the first day of reporting any severity.

- For the onset day of each local reaction, if participants report a change in severity of the local reaction, only the first day of reporting that specific local reaction will be counted.

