3.1.2.2. Systemic Events

The systemic events assessed and recorded in the e-diary are fever, vomiting, diarrhea, headache, fatigue, chills, new or worsened muscle pain, and new or worsened joint pain, from Day 1 through Day 7, where Day 1 is the day of vaccination with qIRV influenza vaccine or licensed QIV.

The derivations for systemic events will be handled in a way similar to the way local reactions are handled for presence of event, severity level, duration, and onset day.

The variables associated with the systemic events will be computed in a way similar to the way local reactions are computed (see [Section 3.1.2.1](#)).

1. Presence (yes or no) of each systemic event on any day (Day 1 through Day 7).
2. Maximum severity of each systemic event on any day (Day 1 through Day 7).
3. Duration of each systemic event.
4. Onset day of each systemic event.
5. Presence (yes or no) of each severe systemic event on each and any of the 7 days.

The symptoms will be assessed by the participant as absent, mild, moderate, or severe according to the grading scale in [Table 6](#) with combined systemic data from both the e-diary and AE CRF. For the systemic analysis, without combining systemic data from the AE CRF, a similar grading scale as Table 6 (without AE CRF data) will be used.

Table 6. Systemic Event Grading Scale

	Mild (Grade 1)	Moderate (Grade 2)	Severe (Grade 3)	Potentially Life-Threatening (Grade 4)^a
Vomiting	1-2 times in 24 hours (from the e-diary) or mild from the AE CRF	>2 times in 24 hours (from the e-diary) or moderate from the AE CRF	Requires IV hydration (from the e-diary) or severe from the AE CRF	Emergency room visit or hospitalization for hypotensive shock Or life-threatening from the AE CRF
Diarrhea	2 to 3 loose stools in 24 hours (from the e-diary) or mild from the AE CRF	4 to 5 loose stools in 24 hours (from the e-diary) or moderate from the AE CRF	6 or more loose stools in 24 hours (from the e-diary) or severe from the AE CRF	Emergency room visit or hospitalization for severe diarrhea Or life-threatening from the AE CRF
Headache	Does not interfere with activity (from the e-diary) or mild from the AE CRF	Some interference with activity (from the e-diary) or moderate from the AE CRF	Prevents daily routine activity (from the e-diary) or severe from the AE CRF	Emergency room visit or hospitalization for severe headache Or life-threatening from the AE CRF

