6.1.2.2. Sensitivity/Supplementary Analyses

To support the assessment of reactogenicity, the endpoints below, as specified in [Section 3.1.2.1](#) and [Section 3.1.2.2](#), will be summarized with the same analysis time point and analysis population:

- Duration (days) of each local reaction and each systemic event after vaccination.
- Onset day of each local reaction and each systemic event after vaccination.

The presentation of the results will include a basic descriptive summary without 95% CIs ([Section 5.2.1](#)).

These continuous endpoints will be summarized by displaying the n, mean, median, standard deviation, minimum, and maximum for each study intervention group by each age group (18 through 64 years of age, ≥ 65 years of age).

In addition, the proportions of participants reporting prompted local reactions and systemic events by maximum severity level with any e-diary errors will be included as a supplemental summary.

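### Setting reaction durations with no known end date to missing drops right-censored values and tends to pull the supplementary duration summaries slightly low

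*SAP*

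**What the plan says.** SAP 3.1.2.1 counts duration from the first to the last day of the reaction, inclusive. A reaction that stops within the diary ends on the last day it was recorded. For one that does not, the SAP uses a later date: "if it is unresolved during the participant e-diary recording period, the date the reaction ends (end date collected on the CRF") or the AE stop date, taking the longer of the two, with an exception for reactions judged chronic. If neither date exists: "If there is no known end date, the duration will be considered unknown and set to" missing. The denominator is participants with the reaction: "Participants with no reported reactions have no duration".

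SAP 3.1.2.2 extends this: "The derivations for systemic events will be handled in a way similar to the way local reactions are handled".

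SAP 6.1.2.2 uses the durations in a supplementary table by study intervention and age group: "These continuous endpoints will be summarized by displaying the n, mean, median, standard deviation, minimum, and maximum". The table has no confidence intervals. The SAP specifies no count of unknown end dates, no lower bound and no time-to-resolution analysis.

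On collection, Protocol 8.3.4 states: "The investigator or designee must obtain stop dates from the participant for any ongoing local reactions, systemic events, or use of antipyretic medication". Protocol 8.3.4.2 adds, for local reactions that outlast the diary, that "the participant will be requested to report that information and the corresponding resolution date". Protocol 8.10.4 (Visit 3) repeats the step: "Collect stop dates of any reactogenicity e-diary events ongoing on the last day that the reactogenicity e-diary was completed".

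**The concern.** Whether a duration is missing depends on the duration itself. A reaction that ends inside the diary supplies its own end date. One still present at the last entry needs a further contact to supply it. When that contact yields no date, the database still shows that the reaction lasted at least from onset to the last day it was known to be present. The SAP discards that information instead of using it. Elsewhere it handles incomplete follow-up by censoring, as in the Cox model of SAP 5.2.3.2.2.

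At stake is a descriptive table that supports a primary safety endpoint. If some prolonged reactions drop out unannounced, the table describes reactions as somewhat shorter than they were, and nothing in it says so.

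**Working it through.** **Which reactions can lack an end date.** The Schedule of Activities (Protocol 1.3) lists obtaining stop dates at Visits 2 and 3 only. Visit 2 is held only for participants who consent to the optional blood sample. For the rest, the one scheduled step is Visit 3, 28 to 35 days after Visit 1. The Visit 4 procedures (Protocol 8.10.5) contain no stop-date step. A reaction still ongoing at Visit 3 therefore has no later scheduled collection of its end.

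Its known minimum is substantial. Visit 3 falls on Day 29 to Day 36 (Visit 1 being Day 1). With onset between Day 7 and Day 1, the minimum runs from 29 − 7 + 1 = 23 days to 36 − 1 + 1 = 36 days. At the other extreme, a reaction that starts on Day 7 and has no later information has a known minimum of 1 day and may in truth be short.

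**No figure to reproduce.** The documents give no expected duration, no share unresolved and no share without an end date. Every value below is an assumption.

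**Effect on the mean.** Let f be the share of reactions unresolved at the end of the diary and m the share of these with no end date. Take mean durations of 2 days (resolved) and 12 days (unresolved).

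- True mean = (1 − f) × 2 + f × 12. With f = 0.03: 1.94 + 0.36 = 2.30 days.
- Mean under the SAP rule = [(1 − f) × 2 + f(1 − m) × 12] / [(1 − f) + f(1 − m)].

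| m | Numerator | Denominator | Reported mean (days) | Change |
|---|---|---|---|---|
| 5% | 1.94 + 0.342 = 2.282 | 0.9985 | 2.285 | −0.6% |
| 10% | 1.94 + 0.324 = 2.264 | 0.9970 | 2.271 | −1.3% |
| 30% | 1.94 + 0.252 = 2.192 | 0.9910 | 2.212 | −3.8% |

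**Wider range.** In general the downward bias is g × (L − S), where g = f × m is the share of all reactions dropped, L their true mean and S the mean of those retained. With S = 2 days and L from 8 to 28 days, the bias is 0.03 to 0.13 days at g = 0.5% and 0.30 to 1.30 days at g = 5%. The latter would need, for example, 10% unresolved and half of those without a date.

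**Median.** If every dropped value lies above the median, the reported median is the 50 × (1 − g) percentile of all durations. For the first and last table rows, g = 0.15% and 0.9%, giving percentiles 49.93 and 49.55. With durations in whole days, the median moves only if a day boundary falls in that narrow gap.

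**Maximum.** It changes only if the longest reaction itself lacks a date.

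**Arms.** A simulation used lognormal durations (median 2 days, log-SD 0.8, rounded up), with 20% of reactions over 7 days losing their end date. Raising incidence from 40% to 80% left the bias among participants with the reaction at −0.09 days in both cases. Only the number of missing durations doubled, from 4.7 to 9.5 per 1,000 vaccinated.

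**The case against.** The strongest reply is that the rule rarely operates and touches little. Reactions that outlast the diary are kept in full when an end date exists. Sites are obliged to obtain that date, and the general duty in Protocol 8.3.4 carries no time limit, so a date may still arrive after Visit 3. The table is supplementary and descriptive, with no test or decision attached. Its n can be compared with the number reporting each reaction in the main analysis (SAP 6.1.2.1). All of this stands and keeps the point small. The comparison of counts does not meet it fully, because a reader would see a gap without learning that it represents ongoing or unknown reactions, or how long they had already lasted.

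Two details narrow the affected set. SAP 5.3.1.1 treats untransferred days of a partly completed diary as no reaction, so a diary that stops early may be read as ending the reaction on its last recorded day. Also, a reaction pooled from the AE CRF without a stop date could be set to missing too. Hence the rule falls mainly, not solely, on reactions unresolved when the diary ends.

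A reader might infer that the rule removes the longest reactions as a class. It does not: long reactions with an end date stay in, and a dropped one may be short. A reader might also infer that the bias is worse in the more reactogenic arm. The documents do not support this. Duration is summarised only among participants with the reaction, so higher incidence alone adds no bias. A difference would need a larger share of long, undated reactions in one arm, or a larger gap between dropped and retained durations. Neither is given. Protocol 4.3 compares qIRV dose groups with each other, not with QIV, and gives no durations.

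**Conclusion.** The point holds as an inexpensive improvement. The SAP deletes right-censored durations that have a known minimum, which tends to lower the mean, standard deviation and maximum in the supplementary tables. The direction follows from the rule, provided the dropped reactions run longer on average than those retained. The size cannot be computed from the documents. Under the stated assumptions (2 and 12 days, 3% unresolved) it is about −0.6% to −4% of the mean for 5% to 30% undated, and the collection steps make the lower part of that range more plausible. No differential effect between arms is shown. The main reactogenicity results on presence and maximum severity are unaffected.

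**What to change.** In SAP 3.1.2.1 and 3.1.2.2, replace the set-to-missing rule: keep a reaction with no known end date as right-censored at the last date it was known to be present. In SAP 6.1.2.2, report the number of reactions with an ongoing or unknown end date by arm and age group. Add either a Kaplan-Meier summary of duration, or the planned descriptive statistics computed with the minimum known duration and footnoted as a lower bound.

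The cost is SAP wording and minor programming; no new data are needed. The minimum-duration option reduces the bias without removing it. In the simulated setting above, with 20% of reactions over 7 days undated and each counted as 8 days, the mean is 3.16 days under the SAP rule and 3.22 days with the minimum, against a true 3.25 days.

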3.1.2.2. Systemic Events

The systemic events assessed and recorded in the e-diary are fever, vomiting, diarrhea, headache, fatigue, chills, new or worsened muscle pain, and new or worsened joint pain, from Day 1 through Day 7, where Day 1 is the day of vaccination with qIRV influenza vaccine or licensed QIV.

The derivations for systemic events will be handled in a way similar to the way local reactions are handled for presence of event, severity level, duration, and onset day.

The variables associated with the systemic events will be computed in a way similar to the way local reactions are computed (see [Section 3.1.2.1](#)).

1. Presence (yes or no) of each systemic event on any day (Day 1 through Day 7).
2. Maximum severity of each systemic event on any day (Day 1 through Day 7).
3. Duration of each systemic event.
4. Onset day of each systemic event.
5. Presence (yes or no) of each severe systemic event on each and any of the 7 days.

The symptoms will be assessed by the participant as absent, mild, moderate, or severe according to the grading scale in [Table 6](#) with combined systemic data from both the e-diary and AE CRF. For the systemic analysis, without combining systemic data from the AE CRF, a similar grading scale as Table 6 (without AE CRF data) will be used.

Table 6. Systemic Event Grading Scale

	Mild (Grade 1)	Moderate (Grade 2)	Severe (Grade 3)	Potentially Life-Threatening (Grade 4)^a
Vomiting	1-2 times in 24 hours (from the e-diary) or mild from the AE CRF	>2 times in 24 hours (from the e-diary) or moderate from the AE CRF	Requires IV hydration (from the e-diary) or severe from the AE CRF	Emergency room visit or hospitalization for hypotensive shock Or life-threatening from the AE CRF
Diarrhea	2 to 3 loose stools in 24 hours (from the e-diary) or mild from the AE CRF	4 to 5 loose stools in 24 hours (from the e-diary) or moderate from the AE CRF	6 or more loose stools in 24 hours (from the e-diary) or severe from the AE CRF	Emergency room visit or hospitalization for severe diarrhea Or life-threatening from the AE CRF
Headache	Does not interfere with activity (from the e-diary) or mild from the AE CRF	Some interference with activity (from the e-diary) or moderate from the AE CRF	Prevents daily routine activity (from the e-diary) or severe from the AE CRF	Emergency room visit or hospitalization for severe headache Or life-threatening from the AE CRF
Fatigue/Tiredness	Does not interfere with activity (from the e-diary) or mild from the AE CRF	Some interference with activity (from the e-diary) or moderate from the AE CRF	Prevents daily routine activity (from the e-diary) or severe from the AE CRF	Emergency room visit or hospitalization for severe fatigue/tiredness Or life-threatening from the AE CRF
Chills	Does not interfere with activity (from the e-diary) or mild from the AE CRF	Some interference with activity (from the e-diary) or moderate from the AE CRF	Prevents daily routine activity (from the e-diary) or severe from the AE CRF	Emergency room visit or hospitalization for severe chills Or life-threatening from the AE CRF
New or worsened muscle pain	Does not interfere with activity (from the e-diary) or mild from the AE CRF	Some interference with activity (from the e-diary) or moderate from the AE CRF	Prevents daily routine activity (from the e-diary) or severe from the AE CRF	Emergency room visit or hospitalization for severe new or worsened muscle pain Or life-threatening from the AE CRF
New or worsened joint pain	Does not interfere with activity (from the e-diary) or mild from the AE CRF	Some interference with activity (from the e-diary) or moderate from the AE CRF	Prevents daily routine activity (from the e-diary) or severe from the AE CRF	Emergency room visit or hospitalization for severe new or worsened joint pain Or life-threatening from the AE CRF

a. Only an investigator or qualified designee is able to classify a participant's systemic event as Grade 4, after clinical evaluation of the participant or documentation from another medically qualified source (eg, emergency room or hospital record). Grade 4 systemic events will be collected on the AE case report form and assessed by the investigator using the AE intensity grading scale.

Oral temperature will be collected in the evening, daily, for 7 days following vaccination (Days 1 through 7, where Day 1 is the day of vaccination) and at any time during the 7 days that fever is suspected. Fever is defined as an oral temperature of $\geq 38.0^{\circ}\text{C}$ (100.4°F). The highest temperature for each day will be recorded in the e-diary.

Temperature will be measured and recorded to 1 decimal place. Temperatures recorded in degrees Fahrenheit will be programmatically converted to degrees Celsius for reporting.

Maximum temperature range over the period from Day 1 through Day 7 will be mapped into the ranges described in Table 7 for summary of maximum temperature. Fever will be grouped into ranges for the analysis according to Table 7 with combined fever data from both the e-diary and AE CRF. For the fever, without combining systemic data from AE CRF, a similar grading scale as Table 7 (without AE CRF data) will be used.

Table 7. Scale for Fever

Mild: $\geq 38.0^{\circ}\text{C}$ to 38.4°C (100.4°F to 101.1°F) from the e-diary or mild grade from the AE CRF
Moderate: $>38.4^{\circ}\text{C}$ to 38.9°C (101.2°F to 102.0°F) from the e-diary or moderate grade from the AE CRF
Severe: $>38.9^{\circ}\text{C}$ to 40.0°C (102.1°F to 104.0°F) from the e-diary or severe grade from the AE CRF
Grade 4: $>40.0^{\circ}\text{C}$ ($>104.0^{\circ}\text{F}$) from the e-diary or life-threatening grade from the AE CRF

Note: Fever is defined as an oral temperature of $\geq 38.0^{\circ}\text{C}$ ($\geq 100.4^{\circ}\text{F}$).

Temperatures $<35.0^{\circ}\text{C}$ and $>42.0^{\circ}\text{C}$ will be excluded from the analysis. If a participant reports a fever (or severity of fever) by accident, the correct temperature will be transcribed in a data handling memo to be included in the analysis, and the temperature that is confirmed as incorrect will not be included in the analysis.

